6.2.3 Accountability and Compliance

Selinexor must be requested by submitting an order form directly to the drug depot and will be shipped directly to site's Investigational Drug Services.

The investigator, or a responsible party designated by the investigator, must maintain an adequate record of receipt, distribution, and return of all study drugs in the form of a Drug Accountability Form. Such records must be provided to the drug supplier upon request.

Subjects are required to bring all used packs and any unused investigational product (IP) when they visit to the site at the end of each cycle. Compliance will be assessed by discussion with the patient and confirmed by pill count. Any deviations and missed doses (including reasons for the deviation or missed doses) will be recorded in the site's internal database and drug accountability logs with the reasons for subsequent verification.

The IP returned by subjects or any unused IP (that is, never dispensed to any subject) must be destroyed after accountability has been performed and only after written authorization from Karyopharm Therapeutics, Inc. has been received.

Subject compliance with the treatment and protocol includes willingness to comply with all aspects of the protocol. The investigator will try to ensure complete compliance with the dosing schedule by providing timely instructions to the patients. In case of non-compliance, the patients will be instructed again. At the discretion of the principal investigator, a subject may be discontinued from the trial for non-compliance with follow-up visits or study drug.

Selinexor should not be used for any purpose outside the scope of this protocol, nor may selinexor be transferred or licensed to any party not participating in the clinical study. Data for selinexor are confidential and proprietary and shall be maintained as such by the investigators.

6.3 Concomitant Medications and Therapies

Concomitant medications include any prescription or over-the-counter preparation, including vitamins, dietary supplements, over-the-counter medications, and oral herbal preparations taken during the study. Patients may continue their baseline medication(s). Any diagnostic, therapeutic, or surgical procedure performed during the study period should be recorded, including the dates, description of the procedure(s), and any clinical findings, if applicable.

6.3.1 Allowed Therapy

Any medication which is considered necessary for a subject's welfare is permitted and may be given at the discretion of the investigator. Medications for treatment of underlying disease and symptomatic treatment of adverse events are permitted. Exceptions are listed in the section below.

Use of Blood Products

During treatment, patients may receive red blood cell (RBC) or platelet transfusions, if clinically indicated, per institutional guidelines.

Appropriate anti-coagulation is allowed during the study (e.g., low molecular weight heparin, direct factor Xa inhibitors, etc.). Warfarin is allowed during the study provided patients are monitored for INR twice a week during the first two cycles of therapy, then weekly to biweekly. Patients may receive supportive care with erythropoietin, darbepoetin, granulocyte-colony stimulating factor or granulocyte macrophage-colony stimulating factor, pegylated growth factors, and platelet stimulatory factors, in accordance with clinical practice or institutional guidelines prior to entry and throughout the study.

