5.1 Inclusion Criteria

Yes/No (Response of "no" = patient ineligible)

- 5.1.1 Male or female subject aged \geq 18 years.
- 5.1.2 Eastern Cooperative Oncology Group (ECOG) performance status \leq 2
- 5.1.3 Diagnosis of primary myelofibrosis (PMF), post-essential thrombocythosis myelofibrosis (also known as thrombocythemia) (PET-MF) or post-polycythemia vera myelofibrosis (PPV-MF).
- 5.1.4 Life expectancy \geq 6 months.
- 5.1.5 Prior treatment with ruxolitinib or any experimental JAK1/2 inhibitor with any one or more of the following:
- Inadequate response after being on \geq 3 months of treatment defined by:
 - Palpable spleen \geq 10 cm below the left subcostal margin on physical examination at the screening visit OR
 - Palpable spleen \geq 5cm below the left subcostal margin on physical examination at the screening visit AND active symptoms of MF at the screening visit defined presence of 1 symptom score of \geq 5 or two symptom scores each of \geq 3 using the Screening Symptoms Form (Appendix 6)
 - Intolerant to ruxolitinib and/or other JAK1/2 inhibitors due to any grade \geq 3 non-hematologic AEs or any grade \geq 2 AEs requiring treatment discontinuation AND palpable spleen \geq 5cm below the left subcostal margin on physical examination at the screening visit.
- 5.1.6 Adequate organ function as defined as:
- **Hematologic** (\leq 28 days prior to C1D1):
 - Total white blood cell (WBC) count \geq 1000/mm³
 - Absolute neutrophil count (ANC) \geq 500/mm³
 - Hemoglobin \geq 7 g/dL
 - Platelet count \geq 30,000/mm³

For patients receiving transfusion and growth factor support, the following delays must be observed between the last administration and hematologic laboratory screening assessments:

- For hematopoietic growth factor support (including erythropoietin, darbepoetin, granulocyte-colony stimulating factor [G-CSF], granulocyte macrophage-colony stimulating factor [GM-CSF], and platelet stimulators [e.g., eltrombopag, romiplostim, or interleukin-11]): at least 2 weeks.

Growth factor support, RBC and/or platelet transfusions are allowed as clinically indicated per institutional guidelines during the study.

- **Hepatic** (\leq 28 days prior to C1D1):
 - Total bilirubin $< 1.5 \times$ ULN except in patients with indirect hyperbilirubinemia due to hemolysis or gilbert's syndrome where total bilirubin should be $< 5X$ ULN
 - Aspartate aminotransferase (AST) and alanine aminotransferase (ALT) $< 2.5 \times$ ULN.

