Grade ≥ 3 with bleeding	
Interrupt selinexor dosing and check platelet counts weekly until the bleeding has stopped, patient is clinically stable and the platelets have recovered to Grade ≤ 3 or baseline. Platelet transfusion is allowed if clinically indicated at the discretion of the principal investigator. When resuming selinexor, reduce by 1 dose level.
 
If recurrent, unless contraindicated, start treatment with moderate to high doses of thrombopoietin stimulating agents as above.

Neutropenia	
Grade 4 neutropenia (afebrile) OR Febrile neutropenia	
Institute colony stimulating factors and prophylactic antibiotics as clinically indicated per institutional guidelines.
 
Interrupt selinexor and check neutrophils at least weekly until recovers to Grade 3 or baseline and without fever (if febrile) and the patient is clinically stable. Colony stimulating factors per institutional guidelines or at the discretion of the principal investigator. When resuming selinexor, reduce by 1 dose level.
 
If recurrent, continue colony stimulating factors, interrupt selinexor until neutrophil counts improve to Grade ≤ 3 or baseline levels. Investigator in consultation with the Medical Monitor may decide to continue selinexor dosing without dose reductions as specified above, provided that CBC and infection symptoms/signs are closely monitored.

Anemia	
Treat per institutional guidelines including blood transfusions and/or erythropoietins. Consider transfusing for symptoms with hemoglobin > 8 g/dL (Grade < 3) or for any Grade 3 (hemoglobin < 8 g/dL). If possible, maintain selinexor dose as long as patient is clinically stable, but if a dose reduction or interruption is desired, it should be done at the discretion of the treating physician and requires authorization from the principal investigator and consultation with the medical monitor if indicated.	
Other clinically significant selinexor-related adverse events	
Grade 1 or 2	Rule out other causes. Maintain dose. Start treatment and/or standard supportive care per institutional guidelines.
Grade 3	
Rule out other causes. Interrupt selinexor until recovers to Grade 2 or baseline and reduce selinexor by 1 dose level.
 
Isolated values of Grade 3 alkaline phosphatase do NOT require dose interruption. Determination of liver versus bone etiology should be made, and evaluation of gamma-glutamyl transferase, 5'-nucleotidase, or other liver enzymes should be performed.

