Change and percentage change in radiographic spleen volume, as well as radiographic spleen response rates, will be summarized using descriptive statistics. The mean, range, standard deviation and 95% confidence interval will be reported for change and percent change in spleen volume.

The proportion of patients with $\geq 50\%$ reduction of total symptoms score will be summarized by observed proportion and exact 95% binomial confidence interval.

The number and proportion of patients with responses per the IWG-MRT criteria will be tabulated and an exact 95% binomial confidence interval for response will be calculated. Overall survival from initiation of therapy to 24 months will be estimated using Kaplan-Meier methods and associated 95% confidence intervals.

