CR	Bone marrow ¹ : Age-adjusted normocellularity; <5% blasts; \leq Grade 1 MF ² and
	Peripheral blood: Hemoglobin \geq 100 g/L and < UNL; neutrophil count $\geq 1 \times 10^9/L$ and < UNL;
	Platelet count $\geq 100 \times 10^9/L$ and < UNL; < 2% immature myeloid cells ³ and
	Clinical: Resolution of disease symptoms; spleen and liver not palpable; no evidence of EMH
PR	Peripheral blood: Hemoglobin \geq 100 g/L and < UNL; neutrophil count $\geq 1 \times 10^9/L$ and < UNL; platelet count $\geq 100 \times 10^9/L$ and < UNL; < 2% immature myeloid cells ³ and
	Clinical: Resolution of disease symptoms; spleen and liver not palpable; no evidence of EMH or
	Bone marrow: ¹ Age-adjusted normocellularity; < 5% blasts; \leq Grade 1 MF ² ; and peripheral blood: hemoglobin ≥ 85 g/L but < 100 g/L and < UNL; neutrophil count $\geq 1 \times 10^9/L$ and < UNL; platelet count $\geq 50 \times 10^9/L$ but < $100 \times 10^9/L$ and < UNL; < 2% immature myeloid cells ³ and
	Clinical: Resolution of disease symptoms; spleen and liver not palpable; no evidence of EMH
CI	The achievement of anemia, spleen or symptoms response without progressive disease or increase in severity of anemia, thrombocytopenia, or neutropenia ⁴
Anemia Response	Transfusion-independent patients: a ≥ 20 g/L increase in hemoglobin level ⁵
	Transfusion-dependent patients: becoming transfusion-independent ⁶
Spleen Response ⁷	A baseline splenomegaly that is palpable at 5-10 cm, below the LCM, becomes not palpable ⁸ or
	A baseline splenomegaly that is palpable at > 10 cm, below the LCM, decreases by $\geq 50\%$ ⁸
	A baseline splenomegaly that is palpable at < 5 cm, below the LCM, is not eligible for spleen response
	A spleen response requires confirmation by MRI or CT showing $\geq 35\%$ spleen volume reduction
Symptoms response	A $\geq 50\%$ reduction in the MPN-SAF TSS ⁹
Progressive disease ¹⁰	Appearance of a new splenomegaly that is palpable at least 5 cm below the LCM or
	A $\geq 100\%$ increase in palpable distance, below LCM, for baseline splenomegaly of 5-10 cm or
	A 50% increase in palpable distance, below LCM, for baseline splenomegaly of > 10 cm or
	Leukemic transformation confirmed by a bone marrow blast count of $\geq 20\%$ or A peripheral blood blast content of $\geq 20\%$ associated with an absolute blast count of $\geq 1 \times 10^9/L$ that lasts for at least 2 weeks
Stable Disease	Belonging to none of the above-listed response categories

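### An anaemia response reached on an erythropoiesis-stimulating agent can count as clinical improvement, so the secondary overall response rate can be inflated

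*Combined protocol and SAP*

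**What the plan says.** **Permission.** Section 6.3.1 states: "Patients may receive supportive care with erythropoietin, darbepoetin, granulocyte-colony stimulating factor". It goes on to other growth factors and allows them "in accordance with clinical practice or institutional guidelines prior to entry and throughout the study". Section 5.1.6 repeats the permission: "Growth factor support, RBC and/or platelet transfusions are allowed as clinically indicated per institutional guidelines during the study". Table 4 in Section 7.2 names ESAs as treatment for anaemia on study: "Treat per institutional guidelines including blood transfusions and/or erythropoietins". None of these places asks for a stable dose or bars a new start.

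**Only timing rule.** For growth factors, Section 5.1.6 says that "the following delays must be observed between the last administration and hematologic laboratory screening assessments", and sets the delay at 2 weeks or more. This concerns the screening blood counts only.

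**Response definition.** In Appendix 5, clinical improvement is "The achievement of anemia, spleen or symptoms response without progressive disease or increase in severity of anemia, thrombocytopenia, or neutropenia". An anaemia response is a haemoglobin rise of at least 20 g/L in transfusion-independent patients. For the others the criterion is "Transfusion-dependent patients: becoming transfusion-independent".

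**Analysis.** Section 10.2.3 counts complete response, partial response and clinical improvement as overall response. Section 11.5.2 says: "The number and proportion of patients with responses per the IWG-MRT criteria will be tabulated", with an exact 95% interval. It does not mention ESAs.

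**The concern.** ESAs are given to raise haemoglobin and reduce transfusion, which are the two things an anaemia response measures. Section 2.1 itself lists erythropoietin among the older supportive treatments used to improve cytopenias in this disease. The 2-week gap before the screening sample suggests that the plan expects these agents to affect the counts, yet nothing comparable applies when response is scored. The gap may even widen the difference: haemoglobin could be sampled off an ESA before entry and scored after the ESA is resumed.

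The Appendix 5 notes do control for transfusion, the other common support. Note 5 uses the pre-transfusion haemoglobin as baseline if blood was given in the previous month, and note 6 bars red-cell transfusion in the response window. A patient whose transfusions are replaced by an ESA can still be scored as transfusion-independent.

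The trial has one arm, so no control group shows how many anaemia responses would occur with supportive care alone. At stake is how far the overall response rate, a named secondary efficacy endpoint, reflects selinexor.

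**Working it through.** **1. The plan's own figures.** The documents give no expected overall response rate, so there is none to reproduce. The only design calculation is for the primary spleen endpoint (Section 11.2), and it checks out:
- Power: P(X ≥ 6 | n = 18, p = 0.42) = 0.837, against 83% stated.
- Type I error: P(X ≥ 6 | n = 18, p = 0.15) = 0.042, within the stated 0.05.
- Enrolment: 18 / (1 − 0.25) = 24, as stated.

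None of these depends on haemoglobin. Primary response is a spleen volume reduction on MRI or CT.

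**2. The route from ESA use to a counted response.**
- ESA use is permitted before entry and throughout (Sections 5.1.6, 6.3.1 and 7.2).
- Anaemia response carries no ESA condition (Appendix 5, table and notes 5 and 6).
- Anaemia response alone can give clinical improvement (Appendix 5).
- Clinical improvement counts in the overall response rate (Section 10.2.3).
- The rate is tabulated with no rule for ESA use (Section 11.5.2).

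No sentence says that responses on ESAs count. That follows because no sentence excludes, flags or separates them.

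**3. What such a patient must still satisfy (Appendix 5).**
- For the 20 g/L rise: baseline haemoglobin below 100 g/L (note 5). Entry is allowed from 7 g/dL, which is 70 g/L (Section 5.1.6), so such patients can enrol.
- For transfusion independence: a rolling 12-week window without red-cell transfusion, ending at haemoglobin of at least 85 g/L (note 6).
- Benefit lasting at least 12 weeks (table header).
- No progressive disease and no worsening of anaemia, thrombocytopenia or neutropenia, with minimum platelet and neutrophil counts (note 4).

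**4. Size.** The efficacy population is every enrolled patient with at least one dose (Section 11.4.2), planned at up to 24. One added responder shifts the rate by 1/24 = 4.2 points.

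For illustration, assume x responders not dependent on an ESA and k patients whose only response is an ESA-supported anaemia response. Both are assumptions. The rate is (x + k)/24, with Clopper-Pearson 95% limits:

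| k | x = 4 | x = 6 |
|---|---|---|
| 0 | 16.7% (4.7 to 37.4) | 25.0% (9.8 to 46.7) |
| 1 | 20.8% (7.1 to 42.2) | 29.2% (12.6 to 51.1) |
| 2 | 25.0% (9.8 to 46.7) | 33.3% (15.6 to 55.3) |
| 3 | 29.2% (12.6 to 51.1) | 37.5% (18.8 to 59.4) |
| 4 | 33.3% (15.6 to 55.3) | 41.7% (22.1 to 63.4) |

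**The case against.** The strongest reply is that few patients could be miscounted. The conditions in step 3 all have to hold together. Section 3.1.4 reports thrombocytopenia at least possibly related to selinexor in 52.1% of patients, and a two-grade platelet decline rules out clinical improvement. An ESA given for anaemia that develops on treatment must first make good that fall and then add 20 g/L over the pretreatment value. The overall response rate is also descriptive, with no test attached, and concomitant medication is reviewed at visits, so ESA use could be described in the report.

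All of this stands and limits the weight of the point. It does not close the gap. The conditions reduce the number of such patients without excluding them, and a handling rule chosen once the responders are known would be post hoc.

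A reader might infer more than the documents support:
- That any patient who starts an ESA and gains 20 g/L is a responder. The baseline, duration and cytopenia conditions say otherwise.
- That the whole rate is biased and cannot be attributed to selinexor. Clinical improvement can also come from a spleen or symptoms response, and a patient with either is a responder whatever the haemoglobin does.
- That every permitted growth factor acts in this way. The haemoglobin mechanism concerns ESAs. Granulocyte and platelet stimulators bear on other thresholds in Appendix 5.

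**Conclusion.** The point holds in conditional form and is minor. As written, the plan can credit selinexor with an anaemia response that an ESA supported, and the secondary overall response rate can be inflated by patients with no other route to response. The primary endpoint, its test and its power are untouched.

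Only the step of 4.2 points per case rests on the plan, and it assumes that all 24 planned patients are dosed. The starting rates of 4/24 and 6/24 and the counts of one to four are illustrations. The true number of such cases is unknown and may be zero, so the documents support saying that the rate can be inflated, not that it is.

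**What to change.** In Section 11.5.2, keep the overall response rate by the named 2013 IWG-MRT criteria and pre-specify a second rate beside it, with its exact 95% interval. The second rate would not credit an anaemia response, or a clinical improvement resting only on one, if during the response period or in the 12 weeks before it an ESA was:
- started;
- resumed after the screening gap; or
- increased, where the dose is recorded.

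A patient who also has a spleen or symptoms response remains a responder. The 12-week look-back is a proposal chosen to match the criteria's own duration requirement. Any interpretation of anaemia benefit should rest on the ESA-excluded figure. The rule should be fixed before the responses are analysed.

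The cost is analysis text and one more tabulation. Section 9 has concomitant medication reviewed at visits, so starts and resumptions should be identifiable. The documents do not say that ESA doses are captured, and Section 13 restricts data capture, so the dose-increase part applies only where the data exist. The downside is a possibly slightly lower attributable response rate, and some genuine drug responses may be left out of the second figure, which is a reason to show both. Supportive care does not change.

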6.3.2 Prohibited Therapy

Concurrent therapy

Concurrent therapy with any approved or investigative anticancer therapeutic outside of those included in this study is not allowed except hydroxyurea. Hydroxyurea is allowed after consultation with medical monitor and PI. Use of any immunosuppressive agents during the study must be confirmed by the Sponsor-Investigator. Treatment that could increase selinexor concentration should be prohibited.

Diet

There are no dietary restrictions on this study. Patients on selinexor should maintain adequate caloric and fluid intake.

Medications

Patients should not take glutathione (GSH)-, S-adenosylmethionine (SAM)-, or N-acetylcysteine (NAC)-containing products during their participation in this study as these products may enhance the metabolism of selinexor. However, they are permitted if the patient has elevated liver function tests.

Given the theoretical potential for GSH depletion, the total dose of acetaminophen should be \leq 1 gram per day on days of selinexor dosing.

6.4 Duration of Therapy

Study subjects may remain on treatment until they experience intolerable toxicities, stop receiving clinical benefit in the opinion of the investigator, or experience IWG-MRT disease progression. Patients who experience IWG-MRT disease progression may continue treatment at the discretion of the investigator if they meet any of the following criteria:

- Subjects are continuing to receive clinical benefit (i.e. symptom improvement and/or anemia response).

- Subject meets progression criteria based solely on spleen size without leukemic transformation (appendix 5).

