Number of Subjects	Up to 24 subjects
Diagnosis and Main Eligibility Criteria	Inclusion: 
• Diagnosis of PMF or PET-MF or PPV-MF• Refractory or intolerant to ruxolitinib and/or any other experimental JAK1/2 inhibitors• Age \geq 18 years, ECOG \leq 2• Life expectancy \geq 6 months• Adequate hepatic, renal, and hematopoietic function Exclusion: 
• Prior exposure to a SINE compound, including selinexor• Radiation, chemotherapy, immunotherapy, or any other anticancer therapy within 2 weeks of C1D1• Major surgery within 4 weeks of C1D1• Uncontrolled active infection requiring treatment, active hepatitis A, B, or C infection• Active gastrointestinal dysfunction affecting absorption or ability to swallow
Study Product, Dose, Route, Regimen	Selinexor, 40-80 mg orally once weekly depending on cohort
Duration of administration	Until IWG-MRT progressive disease criteria for leukemic transformation have been met (appendix 5), subject experiences an intolerable toxicity, or is no clinical benefit per treating physician's discretion, whichever occurs first
Reference therapy	None

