4.4 Study Duration

The estimated duration of enrollment will be 30 months. The primary objective will be evaluated after 6 cycles of selinexor (cycle 7 day 1) treatment. Selinexor treatment will continue thereafter as long as the study drug is tolerated and subject does not meet discontinuation criteria. After discontinuation of the study drug, patients will be followed for survival. It is estimated that each patient will participate in the study for approximately 24 months. Therefore, the estimated study duration is about 60 months.

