6.4.1 Criteria for Discontinuation of Study Intervention

In addition to the drug-specific discontinuation criteria listed in section 7.2, the following will result in treatment discontinuation:

- Subject withdraws consent from the study treatment and/or study procedures. A subject must be removed from the trial at his/her own request. At any time during the trial and without giving reasons, a subject may decline to participate further. The subject will not suffer any disadvantage as a result.
- Any AE that requires a dose interruption > 28 days.
- Unacceptable AE or toxicity that cannot be managed by supportive care.
- Other AEs or intercurrent illnesses which, in the opinion of the investigator, would be injurious to the health or well-being of the subject and warrant their withdrawal from study treatment.
- Necessity for prohibited treatment (as defined in section 6.3) of sufficient dose and duration to confound the study results.
- Sexually active subjects who refuse to use medically accepted barrier methods of contraception (as defined in section 7.4) during the course of the study and for 3 months after discontinuation of study treatment.
- Women who become pregnant or are breastfeeding.
- Significant non-compliance with the protocol schedule or treatment in the opinion of the investigator.
- Subject is lost to follow-up or dead.
- Request by regulatory agencies for termination of treatment of an individual subject or all subjects under the protocol.

Any patient who does not withdraw from the study but who stops attending study visits and does not respond to 3 documented contact attempts will be considered lost to follow-up.

All patients will be followed until disease progression, withdrawal of consent, occurrence of any withdrawal criteria, loss of clinical benefit or intolerable toxicity precluding further treatment with study treatment, death or loss to follow up.

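### The synopsis ends selinexor at leukemic transformation, but Section 6.4 lets a transformed patient with symptom or anemia benefit stay on drug

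*Combined protocol and SAP*

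**What the plan says.** The Study Summary (Duration of administration) gives selinexor "Until IWG-MRT progressive disease criteria for leukemic transformation have been met", or until intolerable toxicity, or until the physician sees no benefit. The list closes with "discretion, whichever occurs first", so transformation is a stop of its own, even if benefit persists.

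Section 6.4 first makes IWG-MRT progression a stop, then adds an exception: "Patients who experience IWG-MRT disease progression may continue treatment at the discretion of the investigator if they meet any of the following criteria". The first criterion is "Subjects are continuing to receive clinical benefit (i.e. symptom improvement and/or anemia response". The second is "Subject meets progression criteria based solely on spleen size without leukemic transformation".

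Section 4.4 says of the period after six cycles: "Selinexor treatment will continue thereafter as long as the study drug is tolerated and subject does not meet discontinuation criteria". Section 6.4.1 opens its list with "In addition to the drug-specific discontinuation criteria listed in section 7.2, the following will result in treatment discontinuation". Neither progression nor transformation appears in that list.

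**The concern.** The two places that set treatment duration disagree about a patient whose disease has become acute leukemia. Two investigators could each follow the protocol and act in opposite ways, and either could be charged with a deviation under the other text. The main stake is patient safety. A smaller one is the primary endpoint: Section 1.1 counts a patient who does not complete six cycles as a non-responder, so the choice of text can decide how an early-transforming patient is classified.

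**Working it through.** No figure in the plan is in dispute, so the check is mainly a comparison of texts.

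**1. Does the exception in Section 6.4 reach transformation?** Yes. Appendix 5 lists leukemic transformation under progressive disease, alongside the spleen criteria.

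**2. Does the limit in the second criterion restrict the first?** No. The criteria are alternatives, and meeting either is enough. Nor does the first criterion require the Appendix 5 category of clinical improvement, which would rule out progressive disease. It asks only for symptom or anemia benefit.

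**3. The texts side by side**

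| Patient with IWG-MRT progression | Study Summary | Section 6.4 |
|---|---|---|
| Spleen only, no transformation | No stop for progression itself | May continue (second criterion) |
| Transformation, no symptom or anemia benefit | Stop | Stop |
| Transformation, with symptom or anemia benefit | Stop | May continue (first criterion) |

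The last row is the conflict.

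**4. Does another rule close the gap?** Three items in Section 6.4.1 come close.
- The adverse event and intercurrent illness item depends on the investigator's opinion.
- The prohibited-treatment item applies only if the patient needs other therapy "of sufficient dose and duration to confound the study results". Hydroxyurea, which Section 6.3.2 allows after consultation, need not trigger it.
- The closing sentence about following patients until progression concerns follow-up and is not a treatment stop.

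**5. When could the primary endpoint be affected?** These inputs come from the Study Calendar and its footnotes.
- C4D1 is day 3 × 28 + 1 = 85, and C7D1 is day 6 × 28 + 1 = 169.
- Scheduled CBCs with differential after the first dose and before C7D1: 3 in cycle 1 (days 8, 15, 22) + 5 × 2 in cycles 2 to 6 = 13.
- Scheduled on-treatment IWG-MRT assessments before C7D1: 1, at C4D1.
- The first scheduled on-treatment marrow is at C7D1 ± 7 days, that is days 162 to 176. It may therefore fall up to 7 days before C7D1.

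These are opportunities to recognise transformation and do not measure harm. For responder status to differ between the texts, four things must coincide: transformation is recognised before six cycles are completed, symptom or anemia benefit persists, the investigator chooses to continue, and spleen volume is down by at least 35% at the primary assessment. Each such patient changes at most one response. A patient found to have transformed after completing six cycles is scored on spleen volume under either text.

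**6. Does the test change?** The rule in Section 11.2 rejects at 6 or more responders of 18, with probability P(X ≥ 6) = Σ C(18,k) p^k (1−p)^(18−k) over k = 6 to 18.
- At p = 0.15: 0.0419, within the one-sided 0.05.
- At p = 0.42: 0.837, against the stated 83%.
- Enrolment: 18 / (1 − 0.25) = 24, as planned.

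The treatment-duration rule enters none of these.

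**7. A secondary, minor point in Section 7.2.** Footnote c of Table 4 says to stop permanently for every Grade 4 non-hematologic event unrelated to selinexor. The Infection paragraph withholds drug for a grade 4 infection and permits resumption at the original dose, whatever the cause. Section 7.2.1 permits dosing to be maintained, after consultation, for grade 3 or higher non-hematological events that Section 7.2 does not list. Footnote c acknowledges neither.

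**The case against.** The best defence is that Section 6.4 already makes progression a stop, so its subsection 6.4.1 had no need to repeat it. The second criterion shows that the authors had transformation in mind. A patient needing leukemia therapy would also ordinarily come off drug, because Section 6.3.2 bars concurrent anticancer treatment apart from hydroxyurea. Part of this stands: the silence of Section 6.4.1 is weak evidence by itself. The conflict remains, because the exception in Section 6.4 overrides its own stop, and the backstops work only by judgement or indirectly.

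It is also fair to say that no precedence rule favours the synopsis, so it could be amended to match Section 6.4 instead. That route is open. But the synopsis and the second criterion both single out transformation, so the omission from the first criterion looks like a drafting slip.

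A reader might infer that footnote c and the Infection paragraph give flatly opposite instructions. The documents do not go that far. The Infection paragraph is permissive, so stopping also complies with it. It is the infection-specific text, Table 4 has no infection row, and Section 7.2 introduces the table as covering other related events. The Infection paragraph is therefore the natural one to govern, and footnote c is only too broadly worded.

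A reader might also take the three-month visit interval after C7D1 as the extra exposure that the conflict causes. It is not. Unrecognised transformation leaves dosing unchanged under both texts, and once transformation is recognised, Section 6.4 sets no limit tied to that interval.

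**Conclusion.** The contradiction is real on the current text: a transformed patient with symptom or anemia benefit must stop under the Study Summary and may continue under Section 6.4. It should be corrected as a matter of patient safety and consistency.

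A reader might infer that the primary result is compromised. The documents do not support that. The effect is confined to transformation recognised before six cycles are completed, at most one response per such patient, and the alpha, power and rejection rule stay as planned. They give no transformation rate, so no probability is offered; that the effect is likely rare is a judgement based on the four conditions having to coincide. The conclusion rests on reading the two criteria in Section 6.4 as true alternatives, which is what their lead-in says. The footnote c point is minor.

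**What to change.** In Section 6.4, limit the exception to IWG-MRT progression without leukemic transformation as defined in Appendix 5, by placing that clause in the lead-in so that it governs both criteria. In Section 6.4.1, add leukemic transformation per Appendix 5 as a discontinuation criterion. Both then agree with the Study Summary.

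In Table 4, state that footnote c is subject to the Infection paragraph and to Section 7.2.1.

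The cost is a clause, a line and a cross-reference, with no new assessments and no change to the endpoint, test or sample size. The one real downside is that a transformed patient who still has symptom or anemia benefit can no longer continue selinexor on study, which the Study Summary already requires. If the clinical team wants to keep that option, the Study Summary should be changed to say so.
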